#### **8.4. SAMPLE SIZE**

The sample size is based on testing the superiority of the high dose of NTRA-9620 compared to placebo on the primary endpoints of percent change in %PN from baseline to time “t” (PC\_PN0-t) where “t” = 12 and 24 weeks. On the basis of historical data, the assumed reduction in PC\_PN0-t is 30% and 42% in placebo and NTRA- 9620, respectively, at both 12 and 24 weeks. A common within-group standard deviation of 20% has been assumed for both arms.

Given the above specifications, and based on the use of a two-sided, two-sample comparison of means at the alpha = 0.025 level of significance, a sample of 45 subjects per group would provide approximately 80% power to demonstrate superiority. Since some subjects may not complete the entire trial, an additional 10% of subjects will be enrolled per arm (50 subjects per arm) to account for this potential loss. Thus, the proposed sample size is 150 subjects.

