Sample Size	
The sample size is based on testing the superiority of the high dose of NTRA-9620 compared to placebo on the primary endpoints of percent change in %PN from baseline to time “t” (PC_PN0-t) where “t” = 12 and 24 weeks. On the basis of historical data, the assumed reduction in PC_PN0-t is 30% and 42% in placebo and NTRA-9620, respectively, at both 12 and 24 weeks. A common within-group standard deviation of 20% has been assumed for both arms.
 
Given the above specifications, and based on the use of a two-sided, two-sample comparison of means at the alpha = 0.025 level of significance, a sample of 45 subjects per group would provide approximately 80% power to demonstrate superiority. Since some subjects may not complete the entire trial, an additional 10% of subjects will be enrolled per arm (50 subjects per arm) to account for this potential loss. Thus, the proposed sample size is 150 subjects. (Note that the protocol provides for a sample size recalculation; the procedure described in the protocol will be followed).

Safety Analysis	The safety analyses will be descriptive and narrative in nature, with SAEs and AEs coded using MedDRA and tabulated by body system, preferred term, treatment group, severity and relation to procedure. Descriptive statistics will be provided by treatment group as appropriate.

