### **8.1.1. Interim Check of Variance Assumption**

This multicenter trial will allow inclusion of a large population of infants from preterm to one year, SBS of varying etiologies, bowel length of varying sizes, presence or absence of ileocecal valve, and varying feeding regimes (e.g., formula only, full or partial own mother's milk). We know of no similar study that has been conducted in such a wide-ranging population - a population that is expected to have especially high variation with respect to prognosis and therefore to study outcome. Our best estimate of within-group variation, which is critical for accurately computing study power, is based on a small pilot study in a related, but not identical, indication. Consequently, we will assess the assumptions used for calculating power by computing the common pooled standard deviation of percent change in %PN when 75 subjects have completed 12 weeks in the study. Should the calculated standard deviation be at least 22% (i.e., 10% greater than the 20% assumed in the protocol), sample size may be adjusted upward accordingly. A statistician blinded to group assignment will compute this interim standard deviation. That statistician will not be involved in any other aspect of the trial. The sponsor will decide whether to increase the sample size during the trial; the decision will be based on the estimated variance but without any knowledge of the interim effect size.

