### **8.1.2. Statistical Tests of Co-Primary and Key Secondary Endpoints**

#### **Co-Primary Endpoint (means)**

The two endpoints (12 weeks and 24 weeks) will each be analyzed using an analysis of covariance model with PC\_PN0-12 and PC\_PN0-24 serving as the dependent variable for each respective analysis. Treatment group and the randomization stratification variables will serve as factors and the baseline %PN value will serve as a covariate in each analysis. In each analysis, the higher dose group will be compared to placebo group first. The high-dose comparison will be tested at the 0.025 two-sided significance level at each timepoint. If the high-dose comparison at a particular timepoint is significant at  $p < 0.025$ , then the low-dose comparison with placebo (at the same timepoint) will be tested at the 0.025 level.

For this endpoint, the Type I error rate will be controlled at 0.05 by using a Bonferroni correction for the two timepoints and a step-down procedure to compare each dose group (high dose first, then low dose) with placebo.

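### The sample size section claims 80% power with 45 per arm at two-sided alpha 0.025; its own inputs give 71–73%, and 45 is the answer for two-sided 0.05

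*Combined protocol and SAP*

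**What the plan says.** Section 8.4 sizes the trial on high dose against placebo for percent change in %PN. The assumed reduction "is 30% and 42% in placebo and NTRA- 9620, respectively, at both 12 and 24 weeks", with a common within-group standard deviation of 20%. For a two-sided test, the section then states: "two-sample comparison of means at the alpha = 0.025 level of significance, a sample of 45 subjects per group would provide approximately 80% power". The synopsis repeats the conclusion that "a sample of 45 subjects per group would provide approximately 80% power to demonstrate superiority". Ten percent is then added for loss, giving 50 per arm and 150 in total.

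The analysis uses the same level. Under Section 8.1.2, "The high-dose comparison will be tested at the 0.025 two-sided significance level at each timepoint", and "the Type I error rate will be controlled at 0.05 by using a Bonferroni correction for the two timepoints".

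Section 8.1.1 plans a blinded check of the pooled standard deviation once 75 subjects have completed 12 weeks. If it is 22% or more, "sample size may be adjusted upward accordingly". No re-sizing formula is given.

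**The concern.** Section 8.4 gives everything needed to check its claim: two means, one standard deviation, the type of test, the level, the sidedness and the sample size. The standardised difference is 12/20 = 0.6, and 45 per arm for 80% power at that difference is the familiar answer for two-sided 0.05. A test at two-sided 0.025 has to need more.

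Two things are at stake. The sponsor, ethics committees and regulators would be relying on a risk of a missed effect that is understated for the comparison described. And the same base may be used for the re-sizing in Section 8.1.1: scaling up from 45 would miss 80% power again.

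**Working it through.** **Inputs** (Section 8.4, with the test level confirmed in Section 8.1.2)

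- Difference: 42 − 30 = 12 points
- Standard deviation: 20 in both arms
- Evaluable subjects per arm: 45, equal allocation
- Two-sided alpha: 0.025, so z = 2.2414; for 80% power, z = 0.8416

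**Attempt to reproduce the stated power**

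Standard error of the difference = 20 × √(2/45) = 4.216.

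Expected test statistic = 12 / 4.216 = 2.846.

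Power (normal) = Φ(2.846 − 2.2414) = Φ(0.605) = **72.7%**.

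Power (two-sample t test, noncentral t, 88 df) = **71.4%**. Pooling the error degrees of freedom over three arms (132 df) gives 71.8%.

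The stated 80% is not reproduced.

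**Sample size needed for 80% at two-sided 0.025**

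n = 2 × [20 × (2.2414 + 0.8416) / 12]² = 52.8, so **53** per arm (normal). The t test needs **55**.

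**Where 45 fits**

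| Test level | n per arm for 80%: normal / t | Power at 45: normal / t |
|---|---|---|
| two-sided 0.025 | 53 / 55 | 72.7% / 71.4% |
| two-sided 0.05 (same n as one-sided 0.025) | 44 / 45 | 81.2% / 80.4% |
| one-sided 0.05 | 35 / 36 | 88.5% / 88.1% |

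Only the middle row matches. Counting all 50 enrolled per arm at two-sided 0.025 still gives only 77.6% (normal) or 76.4% (t).

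**Detectable difference at 45 per arm, 80% power, two-sided 0.025**

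(2.2414 + 0.8416) × 4.216 = 13.0 points (normal); 13.2 points (t).

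**Consequence for re-sizing, if 45 is used as the base**

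At a standard deviation of 22%, scaling gives 45 × (22/20)² = 45 × 1.21 = 54.5, so 55 per arm. Power there at two-sided 0.025 is 73.2% (normal) or 72.1% (t). The requirement for 80% is 2 × [22 × 3.083 / 12]² = 63.9, so 64 (normal), or 66 (t).

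**The second co-primary test**

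Also requiring the Mann–Whitney test at one-sided 0.10 costs essentially nothing. In 20,000 simulated trials with normal data, power was 71.4% with and without it.

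**The case against.** The strongest counter-argument is that the trial succeeds if benefit is shown at week 12 or week 24, so overall power exceeds the power at one time point. With equal effects at both times and 45 per arm, the chance of winning at one or the other is:

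| Assumed correlation, week 12 / week 24 | Normal | t-based |
|---|---|---|
| 0.5 | 86.4% | 85.3% |
| 0.7 | 83.2% | 82.1% |
| 0.8 | 81.2% | 80.0% |
| 0.9 | 78.7% | 77.5% |

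Overall power may well be near 80%. But the documents give no correlation, and Section 8.4 describes a single two-sample comparison at 0.025.

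A second argument is that the analysis is an ANCOVA, which is more precise than the test used for sizing. On the t test, 80% power at 45 per arm needs a residual standard deviation of about 18.2, so covariates explaining 1 − (18.2/20)² ≈ 17% of the variance. That is possible, but the plan does not assume it.

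The variance check does not close the gap either. It acts only at 22% or more, so at the assumed 20% it would change nothing.

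Two cautions do stand. How the slip arose cannot be known: leaving out the Bonferroni split, or treating 0.025 as one-sided, leads to the same 45. And Section 8.1.1 names no formula, so carry-over into re-sizing is a risk, not a demonstrated error.

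**Conclusion.** The concern holds. On the plan's own inputs, 45 evaluable per arm at two-sided 0.025 gives 71–73% power at a given time point, a shortfall of 7 to 9 points that the qualifier in the text does not cover. The trial as sized has 80% power for a difference of 13.0–13.2 points, not 12. This rests only on the stated means, standard deviation, level and sample size; the choice between the normal and t calculations moves the result by little more than one point.

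Type I error control and the treatment estimate are unaffected. What is wrong is a headline claim, made in two places, that could also serve as the base for the interim re-sizing. It should be corrected as a must-fix.

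The 71–73% assumes 45 evaluable. Section 8.1.3 expects about 10% not to reach week 12 and a further 10% not to reach week 24, which would leave about 40 of 50 observed at week 24. Complete-case power there would be about 65–67%. This is indicative only, because multiple imputation is planned.

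**What to change.** 1. **Section 8.4 and the synopsis.** Keep 150 subjects and restate the figure, for example: *With 45 evaluable subjects per arm, a difference of 12 points and a standard deviation of 20%, power is about 71–73% at two-sided alpha 0.025; power is 80% for a difference of 13.0–13.2 points.*
2. **Any other basis for 80%.** If the sponsor relies on success at either time point, or on ANCOVA precision, state the assumed correlation or variance explained and the power that results.
3. **Section 8.1.1.** Specify that any re-sizing is solved at two-sided 0.025 (53–55 evaluable per arm at a standard deviation of 20%, 64–66 at 22%), not scaled from 45.

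The cost is wording in the synopsis and two sections, and a less favourable stated power. No added patients are required. Should the sponsor instead want 80% at each time point, the plan's 10% loss allowance would imply 53/0.9 = 59 to 55/0.9 = 62 per arm, or 177 to 186 in total. That is a separate decision.

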All subjects will receive SOC PN/IV and enteral feedings containing NTRA-9620 or matching placebo. NTRA-9620 or matching placebo will be dosed to target an insulin dose of 1 IU/kg or 2 IU/kg administered four times a day, spaced as equally over 24 hours as possible (ideally at every six hours, but no less than 3 hours between any two doses). The study medications can be reconstituted in normal (0.9%) or half normal (0.45%) saline (NaCl) and administered concomitantly with SOC infant formula, donor breast milk, or own mother's milk (OMM) used for enteral feeds. During the hospitalization period, dosing will be performed as a bolus administration four times a day. In home care, subjects will receive NTRA-9620 or matching placebo four times a day as well.

Subjects will continue treatment for the full 24 weeks of dosing regardless of the %PN use (i.e., even if subject is weaned off PN). Dose interruptions over the 24 week study treatment period will only be allowed at investigator discretion (i.e., nothing by mouth (npo) for procedure.) No dose interruption should last more than 7 consecutive days. During the first 12 weeks when the subject is likely to be hospitalized, the subject should experience no more than 10 days of dose interruption. During weeks 12 to 24, when the subject may be at home or at a secondary facility, the subject should experience no more than 15 days of dose interruption. The daily PN and EN intake for each subject will be recorded in a study diary. Subjects will be assessed weekly or once every two weeks as described on the Schedule of Study Procedures ([Appendix B](#)) for the treatment period. Most subjects will remain hospitalized for at least 12 weeks to collect accurate PN amounts, but some may be released from the institution per local SOC. Subjects will continue treatment for the full 24 weeks of dosing regardless of the %PN use (i.e., even if subject is weaned off PN). Enteral nutrition includes SOC infant formula, donor breast milk, or own mother's milk (as detailed in [Appendix A](#)). Subjects will continue on SOC feedings after the 24 week intervention period. A final study statistical analysis of efficacy and safety will be conducted at Week 28, 4 weeks after the end of dosing. All subjects will be further followed for long-term safety through Week 104; these safety data will be reported as an addendum to the final clinical study report.

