#### **8.1.3. Treatment of Subjects Lost to Follow-up**

Several subjects in this trial may undergo significant interventions during the trial and some may die. Specifically, about 10% of subjects are not expected to reach the 12-week time point for reasons such as death, risk of or actual necrotizing enterocolitis (NEC), or other complications. An additional 10% of subjects are not expected to reach the 24 week time point for similar reasons. Partial data collected from such infants are informative for comparing the treatment arms. For subjects who do not provide any data during the 10-day period for the week 12 or week 24 time point, the endpoint will be imputed using multiple imputation, replacing each missing value with a set of plausible values that represent the uncertainty about the correct value to impute. The multiple imputed datasets will then be analyzed by standard statistical procedures for complete data and combining the results from these analyses. Multiple imputation does not attempt to estimate each missing value through simulated values, but rather to present a random sample of the missing values.

Multiple imputation involves three steps:

1. the missing values are filled in  $m$  times to generate  $m$  complete data sets,
2. the  $m$  complete datasets are analyzed using standard statistical procedures,
3. the results from the  $m$  analyses are combined (using a roll-up estimator) for statistical inference.

The SAP will present full details of the methodology.

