### **8.2.2. Full Analysis Set**

The Full Analysis Set (FAS) will consist of all randomized subjects. Subjects will be analyzed by randomized treatment.

Blind review will be used to assess which interventions undergone during the trial are likely to affect outcome. As noted in the preceding section, major interventions are expected to be independent of treatment.

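### The sample size allows for one 10% loss over the whole trial, but Section 8.1.3 expects 19–20% by week 24, leaving about 40 per arm, not 45, with observed week-24 data (missing endpoints are imputed)

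*Combined protocol and SAP*

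**What the plan says.** Section 8.4 bases the sample size on the high dose against placebo, with means of 42% and 30%, a common SD of 20%, and the same assumptions at weeks 12 and 24. It asks for 45 per group and then adds one allowance for loss: "an additional 10% of subjects will be enrolled per arm (50 subjects per arm) to account for this potential loss". The synopsis makes clear that this allowance is meant to cover the whole study: "Since some subjects may not complete the entire trial, an additional 10% of subjects will be enrolled per arm".

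Section 8.1.3 gives a different expectation. For the first timepoint, "about 10% of subjects are not expected to reach the 12-week time point". For the second, "An additional 10% of subjects are not expected to reach the 24 week time point for similar reasons". The same section says how these subjects are handled: "Partial data collected from such infants are informative for comparing the treatment arms", and where no data exist for the timepoint, "the endpoint will be imputed using multiple imputation". Section 8.2.2 adds: "The Full Analysis Set (FAS) will consist of all randomized subjects". Section 8.5.1 names the FAS and the mITT set for primary testing.

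**The concern.** The same plan contains two loss assumptions, 10% in total and 19–20% in total, and nothing in it reconciles them. The second 10% can be read as a share of all subjects (20% in total) or of those still in the trial at week 12 (19% in total). No reading gives 10% overall.

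Week 24 is a confirmatory timepoint with its own 0.025 test (Section 8.1.2), and Section 8.4 sizes for it explicitly. A reader of 8.4 is told that 50 per arm covers loss over the whole trial. On the plan's own expectation that is true only up to week 12. The gap of about 5 per arm at week 24 is as large as the entire allowance from 45 to 50.

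Nothing later in the plan would correct this. The sample size can be increased if the interim SD is at least 22% (Section 8.1.1) or if too few subjects with less than 50% of bowel are recruited (Section 4.2.3). Neither trigger responds to loss.

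**Working it through.** **Inputs.** Difference 42 − 30 = 12, SD 20, 45 per group, 50 enrolled per arm (Section 8.4). Loss of 10% by week 12 and a further 10% by week 24 (Section 8.1.3).

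**The plan's inflation step.** 45 / (1 − 0.10) = 50. This reproduces and is correct for a total loss of 10%.

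**Observed numbers per arm on the 8.1.3 figures.**
- Week 12: 50 × 0.90 = 45, which matches 8.4.
- Week 24: 50 × 0.80 = 40 (20% in total), or 50 × 0.9 × 0.9 = 40.5 (19% in total).

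**Alpha.** At the stated two-sided 0.025, 45 per group gives 71.4% power (noncentral t) or 72.7% (normal approximation). At two-sided 0.05 it gives 80.4% or 81.2%. That mismatch is a separate matter, so losses are shown at both levels, always as changes from 45 per arm.

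**Complete-case bound at week 24** (unadjusted two-sample comparison of means; t / normal).

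| Observed n per arm | Power, 0.025 | Loss (points) | Power, 0.05 | Loss (points) |
|---|---|---|---|---|
| 45 | 71.4 / 72.7% | – | 80.4 / 81.2% | – |
| 40.5 | 66.1 / 67.7% | 5.2 / 5.1 | 76.0 / 77.0% | 4.3 / 4.2 |
| 40 | 65.5 / 67.1% | 5.9 / 5.7 | 75.5 / 76.5% | 4.9 / 4.7 |

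**With imputation.** For monotone loss 50 → 45 → 40, the effective n per arm at week 24 is

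1 / [(1 − r2²)/40 + (r2² − r1²)/45 + r1²/50],

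where r2 is the correlation of the week-12 with the week-24 outcome, and r1 that of pre-week-12 data with the week-24 outcome. The documents give neither, so both are assumptions shown as a range.

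| r2 | r1 | Effective n | Loss at 0.025, points (t / normal) |
|---|---|---|---|
| 0.5 | 0 | 41.1 | 4.5 / 4.3 |
| 0.5 | 0.3 | 41.5 | 4.0 / 3.9 |
| 0.7 | 0.5 | 43.3 | 1.9 / 1.8 |
| 0.9 | 0 | 44.0 | 1.2 / 1.1 |
| 0.9 | 0.5 | 45.1 | none |
| 0.9 | 0.7 | 46.2 | none |

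At two-sided 0.05 the first row becomes 3.7 / 3.5 points.

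**Either-timepoint rule.** This covers the high dose and the first co-primary endpoint only, complete case, with week 12 held at 45 and week 24 reduced from 45 to 40. The two test statistics are taken as bivariate normal with correlation r × √(n24/n12). For r = 0.5, 0.7 and 0.9 the loss is 1.5, 1.4 and 0.8 points at 0.025, and 1.0, 0.9 and 0.5 points at 0.05. With 40.5 at week 24 it is 1.4, 1.2 and 0.7 points at 0.025. The responder condition is not modelled.

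**The case against.** The strongest reply is that the planned analysis does not lose these subjects. The FAS keeps all 50 per arm, and missing values are imputed at both timepoints. The imputation has material to work with, since Section 3.1 provides that "The daily PN and EN intake for each subject will be recorded in a study diary". Benefit can also be shown at week 12 alone, where the allowance is exact. The either-timepoint figures above are complete-case. With week 24 imputed and week 12 held at 45, the loss at two-sided 0.025 is about 1.2 points (r2 0.5, r1 0), 0.5 (r2 0.7, r1 0.5) and none (r2 0.9, r1 0.5). If early data also predicted week 12, the rule could do slightly better than the plan's 45 and 45. The planned model is ANCOVA, and any gain from adjustment is not counted here. Full imputation detail is left to the SAP, which prevails over the protocol (Section 8.1).

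All of this stands as a limit on the practical effect, but it does not remove the inconsistency. Imputation creates no week-24 observations, and what it recovers depends on correlations that the plan does not state. Section 8.4 does not cite imputation as its reason for allowing only 10%; had full recovery been assumed, no allowance would have been needed. A choice of imputation method in the SAP would not settle which loss expectation is right.

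**Conclusion.** The concern holds. On the plan's own figures, 50 per arm accounts for expected loss at week 12 but not at week 24, where 40 to 40.5 per arm rather than 45 would have observed data. This needs no assumption beyond the two sections themselves.

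The consequence for power is modest. At two-sided 0.025 the week-24 loss after imputation runs from about 4.5 points to none over the assumed correlations (r2 0.5 to 0.9, r1 0 to 0.7), with a complete-case upper bound of 5.1–5.9 points. At two-sided 0.05 the corresponding figures are 3.7 points to none, and 4.2–4.9. For success at either timepoint, the complete-case loss is 0.7–1.5 points at 0.025 and 0.5–1.0 at 0.05. The sponsor should correct this, but it does not threaten the design.

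**What to change.** - Use one loss assumption in Section 8.1.3, Section 8.4 and the synopsis. If the 8.1.3 figures are out of date, correct 8.1.3.
- State the expected number per arm with observed data at each timepoint. On the current 8.1.3 figures that is 45 at week 12 and about 40 at week 24.
- State week-24 power for that number separately from week 12, at the alpha the sponsor confirms. If a gain from imputation is claimed, name the correlations assumed.
- Do not describe 50 per arm as covering loss over the entire trial unless a 10% total is confirmed.

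The cost is wording only, with no added patients. If the 8.1.3 figures stand, the stated week-24 power will be less favourable.

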#### **8.5. STATISTICAL ANALYSIS**

##### **8.5.1. Overview**

Safety and Full Analysis Set (FAS) will be conducted on the safety analysis set. Primary and key secondary efficacy testing will be done using the FAS and the mITT sets. Efficacy testing, including primary and key secondary endpoints, may also be performed on the PP set.

The data will be summarized by group and overall. For continuous data, tables will present means, standard deviations, medians, minima, maxima, appropriate percentiles, and number of

subjects. For categorical data, tables will show counts and percentages. “Time-to-event” data will be summarized using the Kaplan-Meier method. Data listings by subject will be provided.

Statistical analyses will generally be performed using the SAS® system. The effects of noncompliance, dropouts, and possible covariates such as gestational age, birth weight and gender will be assessed as sensitivity analyses.

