### 8.3.3. Key Secondary Endpoint

The trial has the following key secondary endpoint:

Time to reduction of PN to less than 10% of the total caloric intake on each of 14 consecutive days.

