### 8.3.4. Other Secondary Endpoints

The study has the following additional secondary endpoints:

- a) Time to wean off  parenteral nutrition
- b) Number of patients achieving readiness to wean off  at 12 and 24 weeks from baseline
- c) Time to 50% PN/IV reduction from baseline in %PN based on total calories.
- d) Time to 50% PN/IV reduction from baseline in %PN based on volume.

 Baseline: prior to treatment. Baseline measurement period should be at least 7 days.

 Wean off defined as complete cessation of parenteral nutrition and achieving full enteral autonomy for two weeks.

 Reduction to PN of less than 10% of the total caloric intake for two weeks.

- e) Number of patients reaching 50% PN/IV reduction from baseline in %PN based on total calories at 12 and 24 weeks
- f) Number of patients reaching 50% PN/IV reduction from baseline in %PN based on volume at 12 and 24 weeks.
- g) Percent change from baseline in %PN/IV based on total calories.
- h) Percent change from baseline in %PN/IV based on volume.
- i) Percent change from baseline in PN/IV fluid volume during treatment period.
- j) Change in Z-scores (Fenton) from baseline during the treatment period.
- k) Percent change from baseline in %EN based on total calories.
- l) Percent change from baseline in %EN based on total volume.
- m) Change from baseline in liver enzymes (ALT, GGT, and total and direct bilirubin).
- n) Change from baseline in plasma citrulline levels.
- o) Change from baseline in body weight during the treatment period.
- p) Weekly average of hours on prescribed PN/IV during the last month of treatment.
- q) General safety variables including episodes of significant feeding intolerance compared to placebo

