#### **8.5.5.2. Key Secondary Endpoint**

The key secondary endpoint will be analyzed using a stratified log-rank test with factors for treatment group and the randomization stratification variables.

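### Section 8.5.1 summarises the time-to-event endpoints by Kaplan-Meier with no rule for infants who die; cumulative incidence with death as a competing event would report the share reaching each milestone correctly.

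*Combined protocol and SAP*

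**What the plan says.** The key secondary endpoint (Section 8.3.3) is "Time to reduction of PN to less than 10% of the total caloric intake on each of 14 consecutive days". Section 8.3.4 adds three times to event: time to wean off PN (a), and time to a 50% PN reduction by calories (c) and by volume (d). On weaning the footnote reads: "Wean off defined as complete cessation of parenteral nutrition and achieving full enteral autonomy for two weeks".

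The only summary named for such data is in Section 8.5.1: time-to-event "data will be summarized using the Kaplan-Meier method". The test is in Sections 8.1.2 and 8.5.5.2: "The key secondary endpoint will be analyzed using a stratified log-rank test with factors for treatment group and the randomization stratification variables".

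Section 8.1.3 warns: "Several subjects in this trial may undergo significant interventions during the trial and some may die". It puts the losses at two stages. First, "about 10% of subjects are not expected to reach the 12-week time point for reasons such as death", with necrotizing enterocolitis (NEC) and other complications also named. Then, "An additional 10% of subjects are not expected to reach the 24 week time point for similar reasons". For infants with no data at Week 12 or Week 24, "the endpoint will be imputed using multiple imputation"; that covers the percent change in %PN at those weeks, not event times.

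No section gives a censoring rule for death, a competing-risk method or a cumulative incidence estimate. Sections 8.5.5.3, 8.5.6 and 8.5.7 leave the other secondary analyses, the sensitivity analyses and the missing-data methods to the SAP, whose detailed text is not in the public document.

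**The concern.** Death differs from other losses. An infant withdrawn after a complication may still reach <10% PN later, so censoring it has a sensible meaning. An infant who dies cannot. When a death is censored, Kaplan-Meier proceeds as if that infant would have gone on to reach the milestone at the survivors' rate. The estimate then describes a setting without deaths, and 1-KM is larger than the proportion of randomised infants who reach the milestone.

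At stake is how the key secondary curve, the weaning curve and the 50%-reduction curves are read. Clinicians will take their height at Week 24 as the share of infants who got there. The arm comparison is a separate question and is affected only under further conditions, set out below. The co-primary tests do not use Kaplan-Meier.

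**Working it through.** The plan gives no death rate, weaning rate or event count for these endpoints, so there is no stated figure to reproduce. The inputs below are assumptions, shown as ranges.

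**Inputs.** Loss from all causes: 10% + 10% = about 20% by Week 24 (Section 8.1.3). The share due to death is not given, so d = 5%, 10% and 20% are used; 20% would require every loss to be a death. Probability of reaching the milestone by Week 24 in the absence of death: q = 20%, 30% and 50%, assumed. Arm size 50 (Section 8.4).

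**Step 1: independent constant hazards.** Over the 24 weeks, let a = -ln(1-q) and b = -ln(1-d). With deaths censored, 1-KM estimates q. The proportion who actually reach the milestone is

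CIF = a/(a+b) × [1 - (1-q)(1-d)].

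Example, q = 30% and d = 10%: a = 0.3567, b = 0.1054, a/(a+b) = 0.772, bracket = 1 - 0.7 × 0.9 = 0.37, so CIF = 0.772 × 0.37 = 28.6%. The excess is 30.0 - 28.6 = 1.4 points.

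| 1-KM | CIF (excess), 5% deaths | 10% deaths | 20% deaths |
|---|---|---|---|
| 20% | 19.5% (0.5) | 19.0% (1.0) | 18.0% (2.0) |
| 30% | 29.3% (0.7) | 28.6% (1.4) | 27.1% (2.9) |
| 50% | 48.9% (1.1) | 47.7% (2.3) | 45.4% (4.6) |

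**Step 2: deaths only among infants who would not have reached the milestone.** Assume events uniform over Weeks 2-24 with total mass P, and deaths uniform over Weeks 0-24 with mass d. The event density is P/22 and the at-risk fraction Y falls linearly from Week 2 with slope s = P/22 + d/24. In large samples

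1-KM = 1 - exp{-(P/22)/s × ln[Y(2)/Y(24)]}.

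For P = 30% and d = 20%: (P/22)/s = 0.01364/0.02197 = 0.621; Y(2) = 0.983; Y(24) = 0.500; the exponent is 0.621 × 0.676 = 0.420, so 1-KM = 34.3% against a true 30%. At 5% and 10% deaths it is 30.9% and 32.0%. At P = 50% and d = 20% it is 58.1%. The excess can therefore pass the Step 1 figures if deaths are concentrated in this extreme way.

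**Step 3: the log-rank test.** 3,000 simulated trials per scenario, 50 per arm, unstratified log-rank, the same 30% weaning parameter in both arms (q in the independent case, P in the concentrated one), deaths 20% in one arm and 5% in the other. One-sided nominal level 2.5%, taken as a reference because the public text states no level for this endpoint. Simulation error at 2.5% is √(0.025 × 0.975/3000) = 0.3 points.

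| Deaths | Handling | Mean Z | P(Z > 1.96) |
|---|---|---|---|
| Independent | Censored | 0.01 | 2.4% |
| Independent | Held in risk set | -0.24 | 1.4% |
| Only in infants who would not wean | Censored | 0.32 | 4.8% |
| Only in infants who would not wean | Held in risk set | -0.01 | 2.5% |

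Positive Z favours the arm with more deaths. In the third row, 10% against 5% deaths gives mean Z 0.11 and 3.4%. The negative Z in the second row is not an error: that arm's actual share is lower, 27.1% against 29.3%, because more of its infants die first.

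**The case against.** The case against is substantial.

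- **Nothing says that deaths are censored.** A reader might infer from Section 8.5.1 that the plan is simply wrong. The documents do not support that: Kaplan-Meier can also be computed with deaths held as non-events to the end of follow-up. What is established is that the rule is missing and that the usual default is censoring.
- **Detail is left to the SAP.** Section 8.1 calls its account brief and lets the SAP prevail. This stands in part. But the deferrals concern missing data, sensitivity analyses and other secondary endpoints. Death is not a missing event time, and 8.5.1 already names the estimator.
- **The share is already planned elsewhere.** No Week 24 reading of 1-KM is listed as an output. Endpoint (b) counts infants meeting the <10% PN milestone at 12 and 24 weeks, and (e) and (f) do the same for 50% reduction. This stands and lowers the stakes. Time to wean (a) has no matching count, and the plan does not say how deaths enter the counts.
- **The log-rank is a legitimate cause-specific test.** This stands. A reader might infer that an arm with more deaths will look better, or that the direction of a difference could reverse. That needs deaths concentrated in slow-weaning infants, and for an arm contrast, unequal deaths too. Section 8.1.3 makes concentration plausible by grouping death with NEC and other complications, but no figure supports it, and Section 8.2.2 expects major interventions to be independent of treatment.
- **The size is small.** One infant in 50 is 2 points, and the standard error of a difference near 30% is √(2 × 0.3 × 0.7/50) = 9.2 points. This stands.

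**Conclusion.** The point holds as a recommended, inexpensive improvement to a secondary summary. Kaplan-Meier is the only estimator named, deaths are expected, death precludes every one of these milestones, and no rule for it is given.

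If deaths are censored, 1-KM is too high by about 0.5-2.3 points at 5-10% deaths, and by no more than about 4.6 points at 20% deaths. These figures assume constant independent hazards and 1-KM of 20-50%. Full concentration of deaths in infants who would not wean would enlarge the excess, to 8.1 points in the most extreme case computed (58.1% against 50%).

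The between-arm log-rank comparison stays unbiased under independent hazards, even with 20% against 5% deaths. It is distorted only if deaths are concentrated in slow-weaning infants and differ by arm. In the extreme version of that case the one-sided error rate was 4.8% instead of 2.5%. The documents do not show that this will happen, so the finding does not extend to a biased key secondary test.

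**What to change.** In Section 8.5.1 and the SAP:

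1. State how an infant who dies is handled in each time-to-event endpoint.
2. Summarise time to <10% PN, time to wean and both times to 50% reduction by the Aalen-Johansen cumulative incidence function, with death as a competing event.
3. Keep the stratified log-rank as the stated test and label it a cause-specific comparison.
4. Add a supportive version that holds deaths in the risk set as non-events to the end of the efficacy follow-up. Name that day: Section 8.5.8 ends the reported outcomes at 24 weeks, while Section 3.1 and the first footnote to Appendix B place the final analysis at Week 28 (Day 196). Say that this version compares actual shares and so counts extra deaths against an arm.
5. Show deaths by arm beside the curves. Sections 8.5.2 and 8.5.4 already list dropouts with reasons and tabulate SAEs by group, so the data will be to hand.

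The cost is SAP wording, standard software and a little extra analysis work. Reported milestone percentages will be slightly lower. Design, sample size and the co-primary analyses do not change, and Section 8.5.8 has the SAP finalised before data lock, so there is time to do it.
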